2.3 POTENTIAL RISKS AND BENEFITS

2.3.1 KNOWN POTENTIAL RISKS

Human plasma is used as a therapeutic product (Burnouf 2007) and serves as the source material for manufacturing plasma-derived therapeutic products via fractionation, including GRF6021. GRF6021 is a human [REDACTED] fraction [REDACTED] and serves as a viable source of soluble, infusible plasma proteins from healthy male and female donors. It has been [REDACTED] [REDACTED].

GRF6021 has two Important Identified Risks (Hypersensitivity reactions including anaphylaxis and Hypotension and allergic reactions) and one Important Potential Risk (transmission of pathogens).

The overall reporting frequency for hypersensitivity reactions was 0.001% (PSUR). Several steps have been implemented in this study to minimize this risk, including dosing under medical supervision in facilities with adequately trained personnel, access to subcutaneous epinephrine, frequent vital sign measurements during and after each infusion, a 4-hour safety-monitoring period after the end of each infusion, and the exclusion of subjects with a history of allergic reactions to any blood product or IV infusions. In addition, because monitoring beyond the 4-hour period may be required in some cases, all participating study sites will have inpatient facilities available for overnight observation or the ability to transfer the subject to such a facility.

The overall reporting frequency for hypotensive events was 0.002% (PSUR). Several steps have been implemented to minimize this risk, including a slow infusion rate with stepwise increase in rate that can be adjusted to tolerability; frequent monitoring of blood pressure during and after each infusion, guidance on what action to take based on observed changes in blood pressure, and exclusion of subjects with symptomatic orthostatic hypotension. Hypotension is most likely to occur following rapid infusion or intraarterial administration to patients on cardiopulmonary bypass. GRF6021 is contraindicated for use in patients on cardiopulmonary bypass as severe hypotension has been reported [REDACTED] and these subjects are excluded in this study. In the instance of a hypotensive episode, the blood pressure may normalize spontaneously after the slowing or discontinuation of the infusion. If necessary, vasopressors can also be used to correct the hypotension (PI).

Since GRF6021 is made from human plasma, there is a risk that it may contain infectious agents, e.g., viruses, the variant Creutzfeldt-Jakob disease (vCJD) agent, and, theoretically, the Creutzfeldt-Jakob disease (CJD) agent. Since 2006, the total number of infusions administered has been estimated at 466,772, and a total of eleven (11) Individual Case Safety Reports (ICSRs) related to pathogens have been reported; the cumulative risk of pathogen transmission was estimated at 0.002% (PSUR). Several steps have been implemented to minimize the risk that GRF6021 can transmit an infectious agent, including screening plasma donors for prior exposure, testing the donated plasma, and including manufacturing steps, including heat inactivation (heating to 60°C for 10 hours), with the capacity to inactivate and/or remove pathogens.

The capacity of the GRF6021 manufacturing process to inactivate and/or remove viruses was evaluated in viral validation studies designed in accordance with the quality standards established by the European Committee for Medicinal Products for Human Use (CHMP) and the US FDA. Studies were performed using relevant viruses or models of human viruses that represent a wide range of physicochemical properties. Human immunodeficiency virus (HIV) type 1 was used as a relevant bloodborne pathogen, bovine viral diarrhea virus was used to model hepatitis C virus (HCV), and pseudorabies virus was used as a surrogate for large, enveloped deoxyribonucleic acid (DNA) viruses to model hepatitis B virus (HBV) for which there is not practicable assay system. Reovirus type 3 was used to model non-enveloped viruses, hepatitis A virus was used as a relevant non-enveloped virus, and porcine parvovirus was used as a surrogate for human parvovirus B19. The clearance capacities for all individual processing steps that achieved at least 1 log₁₀ were combined to determine the overall clearance capacities, which demonstrate that the manufacturing process for GRF6021 has the capacity to remove and/or inactivate a diverse variety of enveloped and non-enveloped virus challenges and thereby provides assurance that the process yields a margin of safety from the risk of transmission of infectious viruses.

GRF6021 is contraindicated in patients with severe anemia, congestive heart failure, or increased blood volume (PI) and these are exclusion criteria in this study. GRF6021 is depleted of the majority of immunogenic proteins during the manufacturing process, and thus is not expected to alter the blood typing characteristics of the recipient and should not sensitize humans to its subsequent administration [REDACTED]. ABO antigen typing is not required prior to administration. GRF6021 is not expected to significantly alter the urinalyses of recipients, their bleeding times, coagulation times, prothrombin times, prothrombin consumption, platelet counts, or fibrinogen levels when given in quantities of up to 1000 mL [REDACTED].

Based on the cumulative review [REDACTED] (PSUR), the production steps taken to increase the safety margin and avoid virus transmissions, and the multiple safety minimization steps implemented in this study, the benefit-risk balance for GRF6021 as an investigative product in PD-MCI and PDD is favorable.

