5.2 EXCLUSION CRITERIA

An individual will not be eligible for inclusion if any of the following criteria apply:

1. History of blood coagulation disorders or hypercoagulability.
2. Current use of anticoagulant therapy (e.g., heparin, warfarin, thrombin inhibitors, Factor Xa inhibitors). Use of antiplatelet drugs (e.g., aspirin or clopidogrel) is acceptable.
3. Prior hypersensitivity reaction to any human blood product or any IV infusion; any clinically significant known drug allergy.
4. Treatment with any human blood product, including transfusions and IV immunoglobulin, during the 6 months prior to screening.
5. History of immunoglobulin A (IgA) or haptoglobin deficiency, stroke, anaphylaxis, or thromboembolic complications of IV immunoglobulins.
6. Heart disease, as evidenced by myocardial infarction, unstable, new onset or severe angina, or congestive heart failure (New York Heart Association Class II, III, or IV) in the 6 months prior to

- dosing.
7. Presence of signs and/or symptoms of hypervolemia or volume overload, including but not limited to pulmonary edema and/or clinically significant peripheral edema.
 8. Patients with recent or planned surgery sensitive to blood volume changes including cardiopulmonary bypass technique.
 9. Poorly controlled high blood pressure (BP) (systolic BP of 160 mmHg or higher and/or diastolic BP of 100 mmHg or higher) despite treatment during the 3 months prior to dosing, or treatment refractory high BP, defined as treatment requiring 3 or more antihypertensives from different classes.
 10. Supine hypertension (systolic BP of 160 mmHg or higher and/or diastolic BP of > 90 mmHg when in a supine position).
 11. Symptomatic orthostatic hypotension (drop in systolic BP of 20 mmHg or higher, or 30 mmHg in the presence of essential hypertension, and/or a drop in diastolic BP of 10 mmHg or higher, after 3 minutes of standing despite adequate hydration); symptoms can include, but are not limited to, lightheadedness, visual blurring, dizziness, and/or syncope.
 12. History of Torsades de Pointes dysrhythmia.
 13. Clinically significant abnormalities on screening electrocardiogram (ECG) including QTc intervals (using Fridericia's correction formula) of ≥ 450 ms in men and ≥ 470 ms in women.
 14. Clinically significant abnormalities on echocardiogram.
 15. Hypocalcemia of any kind, including secondary to absorption syndromes related to gastric bypass surgery.

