7.1.1.1.10 Echocardiogram

During screening, an echocardiogram will be performed to evaluate the subject's left ventricular (LV) systolic function to ensure the subject's ejection fraction percentage is $\geq 55\%$ ([Gebhard 2012](#)).

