3. GENERAL INFORMATION

- GRF6021 is contraindicated in subjects with anemia, increased blood volume, or congestive heart failure, and in subjects on cardiopulmonary bypass. Note: ejection fraction as measured with echocardiography should be performed at screening to determine eligibility before dosing occurs.
- During the dosing periods, Pre-infusion Safety Labs will be drawn locally before the infusion starts. These labs must be reviewed before dosing the follow day. The following blood labs must be documented as within normal limits: sodium, potassium, ionized calcium, blood urea nitrogen, creatinine, hematocrit, hemoglobin, and platelets. Pregnancy testing will be required prior to dosing on Visits 3 and 11 in women of childbearing potential (WOCBP).
- The use of a volumetric infusion pump is the preferred method of administration of study drug. The study drug may be infused by gravity with a rate controlling device if a pump is not available or is not operational. The PI or designee must approve this infusion methodology for each individual subject. If a rate-controlling device is used, it must be continuously monitored by the unblinded Infusion Nurse.
- Study drug administration should be performed in a controlled clinical setting such as a physician’s office, Phase 1 unit, or Ambulatory Infusion Center (AIC).

- An appropriately qualified blinded Outcomes Assessor will monitor the subject throughout the infusion and for approximately 4 hours after the infusion has been completed. This person’s qualifications must enable them to identify AEs, monitor vital signs, and take the appropriate course of action when an AE or clinically-significant vital sign change occurs.
- Sites must identify and follow procedures that ensure adequate blinding of blinded study personnel, subjects, and trial partners before, during, and after the Infusion Period. This may include the use of study drug container covers and/or the use of drapes to separate the unblinded Infusion Nurse and infusion apparatus from the blinded Outcomes Assessor, PI, subject, and trial partner.
- The unblinded pharmacist, or other qualified site personnel responsible for drug accountability, must retain all used vials/containers for drug accountability, unless otherwise agreed to with the Sponsor. These should be kept in a secure location with limited access to minimize the risk of unblinding blinded study staff. Partially-used vials/containers may not be re-used.

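### Section 2.3.1 of the protocol says congestive heart failure is excluded, but exclusion 6 bars only NYHA Class II–IV failure in the 6 months before dosing, so no criterion bars a current, compensated Class I diagnosis

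*Protocol*

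**What the plan says.** Section 2.3.1 (Known Potential Risks): "GRF6021 is contraindicated in patients with severe anemia, congestive heart failure, or increased blood volume (PI) and these are exclusion criteria in this study". Appendix 11, section 3 (General Information): "GRF6021 is contraindicated in subjects with anemia, increased blood volume, or congestive heart failure, and in subjects on cardiopulmonary bypass". Neither sentence limits heart failure by class or by time.

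Section 5.2, exclusion 6, covers recent heart disease. Its heart-failure part reads "congestive heart failure (New York Heart Association Class II, III, or IV) in the 6 months prior to" dosing. No other criterion in sections 5.1 or 5.2 names heart failure.

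Several other criteria bear on the same subjects:

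- Inclusion 11 requires an ejection fraction of at least 55%.
- Exclusion 7: "Presence of signs and/or symptoms of hypervolemia or volume overload, including but not limited to pulmonary edema and/or clinically significant peripheral edema".
- Exclusion 13: "Clinically significant abnormalities on screening electrocardiogram (ECG) including QTc intervals" above stated limits.
- Exclusion 14: "Clinically significant abnormalities on echocardiogram".
- Exclusion 27 leaves any other safety concern to the investigator.

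Appendix 11, section 3 follows its contraindication with a note that "ejection fraction as measured with echocardiography should be performed at screening to determine eligibility before dosing occurs".

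**The concern.** Section 2.3.1 tells investigators, ethics committees and regulators that heart failure is excluded. Section 5.2, which sites apply when they enrol, implements only part of that exclusion. By attaching three NYHA classes to the diagnosis, exclusion 6 signals to a site that Class I is allowed. The 6-month window adds to this: a subject who was Class II seven months ago and Class I since then also passes.

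What is at stake is subject safety. The product is iso-oncotic with plasma (section 6.1.2) and is infused on 5 consecutive days in each of two periods. Section 8.4.3 makes clinically significant peripheral or pulmonary edema an event of special interest, so the protocol itself treats fluid overload as a concern. Section 2.3.1 rests its favorable benefit-risk conclusion partly on the study's risk-minimization steps, and section 2.3.2 says no benefit is known in this population.

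**Working it through.** The plan gives no figure to reproduce, so the check sets the stated exclusion against each criterion that could deliver it.

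**Step 1. The three contraindications in section 2.3.1 and their criteria**

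| Contraindication | Criterion | Limits |
|---|---|---|
| Severe anemia | Exclusion 20 | Hemoglobin below 10 g/dL (women) or 11 g/dL (men) |
| Increased blood volume | Exclusion 7 | No class or time limit |
| Congestive heart failure | Exclusion 6 | NYHA II, III or IV only; 6 months before dosing only |

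Only heart failure is narrowed by both class and time.

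**Step 2. Test case: a current heart-failure diagnosis, Class I for the past 6 months, compensated**

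- Exclusion 6: passes, because Class I is not named.
- Inclusion 11: passes if the ejection fraction is at least 55%. Section 7.1.1.1.10 describes this echocardiogram as an assessment of left ventricular systolic function, so this criterion does not screen out failure with preserved ejection fraction.
- Exclusion 7: passes if there are no signs or symptoms of overload.
- Exclusions 13 and 14: passes if nothing clinically significant is found. Exclusion 14 is not confined to ejection fraction, so it will remove some preserved-fraction cases, but it depends on a judgement of significance.
- BNP: measured in the screening panel (section 7.1.1.1.11), but no cut-off is given. Exclusion 18 lists nine items (complete blood count, complete metabolic panel, albumin, lipids, coagulation, thiamine, pyridoxine, cobalamin, thyroid stimulating hormone), and BNP is not one of them. It can act only through exclusion 27.
- Exclusion 27: bars the subject only if the investigator so decides.

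The subject passes every criterion except the discretionary one.

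**Step 3. Safeguards outside the eligibility criteria**

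- Appendix 11, section 3: the unqualified contraindication is in front of staff at dosing.
- Appendix 11, section 5.2: history and diagnosis are checked, and the principal investigator clears the subject, before infusion.
- Section 7.3.4: heart, lung and edema examination before infusion at Visits 3, 5, 7, 11, 13 and 15, and weight at every infusion visit.
- Appendix 11, section 4.4: infusion starts at 30 mL/hour and is stepped up.
- Appendix 11, section 6, Table 3: signs or symptoms of volume overload stop the infusion, with no restart and no further dosing.

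These reduce the risk, but none is an eligibility criterion. The Table 3 rule acts only once overload has appeared.

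**Step 4. Size**

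The documents give no prevalence of Class I failure in this population, so the size of the group cannot be computed. What can be said is who would be exposed: about 60 of the 90 randomized subjects receive GRF6021, and the other 30 receive saline.

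**The case against.** The strongest reply is that section 2.3.1 is a background summary and section 5.2 is its operational form. On that view severe anemia becomes hemoglobin cut-offs, increased blood volume becomes exclusion 7, and heart failure becomes exclusion 6. The contraindication is attributed to a source cited as PI (apparently the product information), which is not among the documents. Whether exclusion 6 departs from that source cannot be judged, and that much stands. The point rests only on the protocol's own statement that heart failure is an exclusion criterion, which section 5.2 does not fully carry out.

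A second reply is that the uncovered subject must meet a chain of narrow conditions, and that an investigator following Appendix 11 holds an explicit contraindication with no class limit. This also stands, and it limits the weight of the point. It does not remove the mismatch, because the contraindication in Appendix 11 is not written as an eligibility rule and the note attached to it directs staff to ejection fraction.

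A reader might infer more than the documents support:

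- **That heart-failure patients are broadly admitted.** They are not. Recent Class II–IV failure, an ejection fraction below 55% and overt overload are all barred by rule.
- **That bare investigator discretion is the only protection.** Step 3 of the working shows otherwise.
- **That a chance of enrolling such a subject can be quoted.** Any such figure would rest on an assumed prevalence with no basis in the documents, and counting all 90 subjects would wrongly include those on placebo.

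**Conclusion.** The mismatch is clear from the text. Section 2.3.1 and Appendix 11 state the heart-failure contraindication without limit, section 2.3.1 adds that it is an exclusion criterion, and exclusion 6 delivers only the Class II–IV, 6-month part. No eligibility criterion bars a current Class I diagnosis with preserved ejection fraction, no overload, and no clinically significant ECG or echocardiogram finding.

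The consequence is small. The group is probably very small and may be empty, and the dosing safeguards would limit harm to anyone in it. Confidence is high in the inconsistency; the documents do not show that any subject would be harmed. Sample size, error rates, analysis and the randomized comparison are not affected. The correction is still worth making, because it costs little and makes the criteria deliver a safety exclusion that the protocol says it already has.

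**What to change.** Reword exclusion 6 in three parts:

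- (a) The myocardial infarction and angina conditions already listed, within 6 months before dosing, unchanged.
- (b) A current diagnosis of congestive heart failure of any NYHA class, including compensated or treated failure.
- (c) NYHA Class II, III or IV heart failure at any time in the 6 months before dosing, even if since resolved.

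Part (c) keeps the present bar and is needed. With (a) and (b) alone, a Class III episode four months ago that is now recorded as resolved would pass, and the criterion would be looser than it is today. A resolved diagnosis outside the 6-month window need not be barred.

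If the sponsor means to allow compensated Class I failure, it should leave exclusion 6 as it is, and qualify and justify this in section 2.3.1 and in Appendix 11, section 3.

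The cost is one reworded criterion in an amendment and possibly a few more screen failures. No new test is needed, because the screening medical history (section 7.1.1.1.4) already collects current and past conditions.

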2.3.2 KNOWN POTENTIAL BENEFITS

There is no known reported benefit of administering GRF6021 to patients with PD-MCI or PDD.

3 OBJECTIVES AND PURPOSE

The primary objective of this study is to assess the safety and tolerability of GRF6021, a [REDACTED] human [REDACTED] fraction administered by IV infusion, in subjects with PD and cognitive impairment. Secondly, this study aims to assess the effects of GRF6021 on subjects' cognitive and motor function. Exploratory objectives include blood and plasma collection to identify specific biomarkers associated with cognitive and motor changes and/or indicators of PD-MCI and PDD progression. In addition, MRI of the brain will be conducted after the second treatment period in consenting subjects to identify potential therapeutic effects of GRF6021.

4 STUDY DESIGN AND ENDPOINTS

4.1 DESCRIPTION OF THE STUDY DESIGN

This will be a randomized, double-blind, placebo-controlled study conducted at up to 40 sites in the US and ex-

US.

During the screening period (Day -35 through Day -8), subjects will undergo all screening assessments, including a screening MRI and an echocardiogram, and complete two training sessions on the Continuity and Power of Attention, Working Memory, and Episodic Memory on the CDR-CCB. During the Baseline Visit (Day -7 through Day -1), subjects will complete cognitive and motor testing. Subjects will then be randomized in a 2:1 ratio to GRF6021 (Group 1) or placebo (Group 2).

There will be two (2) dosing periods. Each dosing period (Treatment 1, starting at Week 1; and Treatment 2, starting at Week 13) consists of 5 consecutive days (“pulsed dosing”) of IV infusions of [REDACTED] of either GRF6021 or placebo. During each 5-day treatment period, the administration of GRF6021/placebo will occur in a setting with appropriate medical monitoring by adequately trained personnel. The infusions can occur in the inpatient/hospital setting or in an outpatient infusion center or equivalent medical facility. Following a 4-hour post-infusion monitoring period, the subject may return home if medically stable based on the investigator’s clinical judgement. Should further monitoring be required, subjects may need to remain at and/or be transferred to an appropriate facility for extended outpatient monitoring and/or inpatient observation.

Safety and tolerability assessments will occur at every visit. Cognitive and motor testing will be performed at Baseline and at periodic interim visits following dosing. Cognitive and motor testing may take up to approximately 2.5 hours. It is preferred that the sequence of tests administered should be consistent for all subjects. Subjects (and/or their trial partners, if applicable) may take breaks between assessments as needed.

In the event of early termination of a subject who has received at least one infusion, the end of study procedures will be performed unless the subject has withdrawn consent. A comprehensive efficacy and safety assessment of all data *in toto* will be conducted at the end of the study.

Subjects will also be invited to participate in an additional MRI obtained at Visit 16 to detect potential changes in brain atrophy, cortical thinning, functional connectivity, and cerebral blood flow after treatment. The MRI procedure, as well as the potential risks and benefits, will be explained to all study participants. Participation in the Visit 16 MRI scan is optional and not required for inclusion in the study.

The overall duration of the study/recruitment period is approximately 24 months from study initiation (i.e., following consent of first subject) to study completion (i.e., last subject, last visit). The subject participation period is approximately 7 months from Screening through End of Study, unless prematurely discontinued.

4.2 STUDY ENDPOINTS

4.2.1 PRIMARY ENDPOINT

Primary Endpoint:

- Incidence of TEAEs and SAEs identified by MedDRA PT and grouped by MedDRA SOC.

4.2.2 SECONDARY ENDPOINTS

This study is not powered to detect statistically significant differences in cognitive or motor domains between

the Baseline and End of Study values. Secondary endpoints will be summarized over the study period from Baseline values using descriptive statistics.

Secondary Efficacy Endpoints:

- Change from baseline in the MoCA (Nasreddine 2005)(Appendix 1).
- Change from baseline in Continuity and Power of Attention, Working Memory, and Episodic Memory on the CDR-CCB (Wesnes 1977, Wesnes 2000).
- Change from baseline in D-KEFS Verbal Fluency (Delis 2001, Delis 2004, Emre 2004).
- Change from baseline in the MDS-UPDRS 1, 2, 3, and total score (Fahn 1987, Movement Disorders Task Force 2003)(Appendix 2).
- Change from baseline in the SE-ADL Scale (Schwab 1968)(Appendix 3).
- Change from baseline in the CISI-PD (Martinez-Martin 2006)(Appendix 4).
- Change from baseline in the PDQ-39 (Peto 1998)(Appendix 5).
- Change from baseline in the GDS-15 (Yesavage 1983)(Appendix 6).
- Change from baseline in the dCDT (Müller 2017).

Secondary Safety Endpoints:

- Change from baseline in clinical laboratory parameters.
- Change from baseline in vital sign measurements.
- Change from baseline in body weight.
- Change from baseline in the S-STs (Sheehan 2014)(Appendix 7).

